7.6. Study Supplies and Device Accountability

The Barrx™ Flex Radiofrequency Ablation System will be provided to each site upon Sponsor collection and approval of all required regulatory documentation. Up to 8 catheters per patient (including both

balloon catheters and focal catheters) may be used during the study protocol (including both treatment phase and follow-up phase). This number may be exceeded depending on extent of disease during follow-up and the number of energy applications needed per session. The device should be stored in a secure (locked) area under the appropriate storage conditions. The study devices shall be used according to the CIP. Access should be limited to designated study staff only. Device accountability logs will be provided to the site. It is the site's responsibility to document the receipt date, device identification, disposition of the product (per subject use including date, including amount used, amount remaining, etc.), transfer (if applicable) and return of all unopened expired or malfunctions study devices.

8. Selection of Subjects

8.1. Study Population

The study cohort will be subjects with early ESCN, defined as MGIN or HGIN.

8.2. Subject Enrollment

Up to 100 subjects are planned for enrollment in the primary analysis cohort. With up to 10 sites and 1-2 endoscopists at each site, up to 50 'run-in' patients will be included in this study. Run-in patients are defined as up to 5 patients for each endoscopist that is inexperienced with RFA or has had no RFA onsite training from CICAMS. Data from the run-in patients will be analyzed separately from the cohort.

Patients shall be reviewed according to the following inclusion and exclusion criteria. An answer of "no" to any inclusion criterion or an answer of "yes" to any exclusion criterion disqualifies a subject from participating in this study. Complete the **Eligibility CRF**.

Definitive eligibility can only be assured during the primary RFA endoscopy, e.g. if a severe stricture or a non-flat abnormality is present, patient is not eligible. Therefore, the subject is considered as enrolled after insertion of the RFA catheter.

8.3. Inclusion Criteria

1. Patient is 18-85 years of age
2. Patient has evidence of ESCN, within the last 3 months, patient demonstrated a new diagnosis or a reconfirmed diagnosis of squamous MGIN and/or HGIN of the esophagus
3. On endoscopic examination, subject has at least one USL that measures at least 3 cm in at least one dimension and greater than $\frac{1}{4}$ of the esophageal circumference and has MGIN or HGIN on biopsy, confirmed by central pathologist

4. All lesions in the esophagus are completely flat (Paris type 0-IIb), both on WLE and Lugol's chromoendoscopy
5. The maximum allowable linear length of "USL-bearing esophagus" is 12 cm
6. Baseline endoscopic ultrasound (EUS) (if applicable) shows no exclusionary findings for the trial
7. Computed Tomography (CT) scan of chest and upper third of the abdomen (if applicable) shows no exclusionary findings for the trial
8. Based on the judgment of the study endoscopist, the patient is eligible for treatment, follow-up endoscopy, and biopsy as required by the protocol
9. EMR or ESD occurred > 3 months before enrollment, patients may be eligible for the study if procedure was curative (negative margins and no risk of lymph node involvement) and the patient has no other findings concerning for cancer
10. The subject is willing to provide written, informed consent to participate in this clinical study and understands the responsibilities of trial participation

8.4. Exclusion Criteria

1. Patient has esophageal squamous cell carcinoma (ESCC)
2. Any non-flat (Paris type 0-I, 0-IIa, 0-IIc, 0-III) abnormalities anywhere in the esophagus
3. Any abnormalities under WLE, Lugol's chromoendoscopy or NBI that are suspicious for ESCC anywhere in the esophagus (e.g. 'pink sign' USL, defined as a color change after Lugol's staining: initially whitish yellow and pink 2-3 minutes later)
4. Any USL with MGIN or worse on biopsy outside the treatment area
5. Esophageal stricture preventing passage of a therapeutic endoscope
6. Prior endoscopic mucosal resection (EMR) or endoscopic submucosal dissection (ESD) which occurred < 3 months before enrollment
7. Any esophageal dilation in the past 12 months
8. Any history of a non-squamous cell cancer of the esophagus, or any history of a squamous cell cancer of the esophagus (any stage)
9. Any previous ablative therapy within the esophagus (photodynamic therapy, multipolar electrical coagulation, argon plasma coagulation, laser treatment, or other) or any radiation therapy to the esophagus
10. Previous esophageal surgery, except fundoplication without complications (i.e., no slippage, dysphagia, etc.)
11. Evidence of esophageal varices detected within last 6 months or at initial RFA procedure
12. Patient has active reflux esophagitis grade C or D
13. Evidence of eosinophilic esophagitis on endoscopy and/or histology
14. Inner diameter of the esophagus measuring <18 mm
15. Report of uncontrolled coagulopathy with international normalized ratio (INR) > 2 or platelet count <75,000 platelets per μL (note: a complete blood count is not required for all subjects in this study)
16. Patient is using anti-thrombotic agents that cannot be discontinued 7 days before and after therapeutic sessions
17. Patient has an implantable pacing device (examples: automated implantable cardioverter defibrillator, neurostimulator, cardiac pacemaker) and has not received clearance for enrollment in this study by specialist responsible for the pacing device
18. Patient has life expectancy less than 5 years
19. Patient suffers from psychiatric or other illness and/or has a known history of unresolved drug or alcohol dependency that would limit ability to comprehend or follow instructions related to informed consent, post-treatment instructions, or follow-up guidelines
20. Patient is considered to be part of a vulnerable population (e.g. prisoners or those without sufficient mental capacity)
21. The subject has participated in an investigational drug or device research study within 30 days of enrollment that would interfere with this study
22. Patient is pregnant or has plans to become pregnant in the ensuing 12 months (confirmation of non-pregnant status in women of child-bearing age and ability required with urine or blood test to be eligible)

9. Study Procedures

9.1. Schedule of Events

For patients who meet all of the inclusion criteria and none of the exclusion criteria, step-wise endoscopic RFA will be performed in 3month intervals \pm 4 weeks from the first RFA per the Patient Flow Diagram (Figure 1). Each decision point in the flow diagram regarding endoscopy, staining, RFA, biopsy, and patient advancement to subsequent study visits is fully delineated in the diagram. The study primary endpoint biopsies are obtained at 12 months from the initial treatment.

Study procedures are summarized in Table 2 and described in detail below.

Table 2. Study Schedule and Assignments

	BQE (1 week to 3 months before first RFA)	Baseline assessmen ts	Primary RFA	3-Month Follow-Up visit (from primary RFA, \pm 4 weeks)	6-Month Follow-Up Visit (from primary RFA, \pm 4 weeks)	9-Month Follow-Up Visit (from primary RFA, \pm 4 weeks)	12-Month- Primary Endpoint (from primary RFA, \pm 4 weeks)	2-3-4-5 Year Follow-up (from primary RFA, \pm 4 weeks)
	BQE is part of regular care		After insertion of RFA catheter, patient is considered enrolled in the study: treatment phase					Follow-up phase
Informed Consent		X						
Patient History CRF		X						
Baseline Qualifying CRF		X						
Confirmation of Study Eligibility CRF		X						
Upper Endoscopy using Lugol's Solution	X			X	X	X	X	X
Circumferential RFA at 12 J/cm ²			X					
Endoscopy CRF			X	X	X	X	X	X
Table of findings CRF			X	X	X	X	X	X

Medtronic Confidential

COVB3050540 (REACH) Clinical Investigation Plan

Version 7.0

15-Mar-2018

Page 26 of 62

	BQE (1 week to 3 months before first RFA)	Baseline assessmen ts	Primary RFA	3-Month Follow-Up visit (from primary RFA, +/- 4 weeks)	6-Month Follow-Up Visit (from primary RFA, +/- 4 weeks)	9-Month Follow-Up Visit (from primary RFA, +/- 4 weeks)	12-Month- Primary Endpoint (from primary RFA, +/- 4 weeks)	2-3-4-5 Year Follow-up (from primary RFA, +/- 4 weeks)
Circumferential or focal RFA at 12 J/cm ²				X	X	X		X
Biopsy	X			X	X ¹	X ¹	X	X
Central pathology review (BQE biopsy)		X						
Central pathology review				X	X	X	X	X
2 nd pathologist assessment		X					X	X ²
Pathology CRF		X		X	X	X	X	X
Study Exit CRF								X ⁴
Safety Assessment			X	X	X	X	X	X
Observation of endoscopy by CICAMS expert			X	X	X	X	X	X
Keyhole biopsy if diagnosis of suspicious/visible lesion needed before escape treatment				X	X	X	X	X
Escape treatment (see section 9.4.3) for ESCC/ disease suspicious for ESCC				X	X	X		X
Escape treatment if residual ESCN							X	X ³

Remarks:

¹ Biopsies at 6 and 9 months will be performed only if USL are detected after CR

Medtronic Confidential

² Only recurrent or progressive disease during FU will be assessed by a second expert pathologist. This includes biopsies indicating recurrent or progressive disease, and eventual EMR/ESD/surgery specimens.

³ If persistent after 4 additional RFA sessions

⁴ Study completion is defined as when all follow-up visits have been completed, all data has been entered, reviewed, monitored, and database has been locked.

9.1.1. Tissue Specimen Processing and Histopathological Interpretation

In order to ensure uniform tissue specimen preparation, staining technique, and histopathological evaluation, all study tissue specimen processing using the same laboratory practices. All slides will be stained with hematoxylin and eosin.

All baseline tissue specimens obtained from the esophagus will be independently reviewed by two expert GI pathologists at the lead study site (CICAMS) to confirm eligibility per the inclusion and exclusion criteria. Eventual discrepant results will be resolved by joint reading. All results are entered on the pathology CRF.

All biopsies obtained after the initial RFA procedure at any time of the study will also be reviewed by the lead study site pathologist. This includes biopsies from all USLs, biopsies from a normal staining post-RFA esophagus to confirm CR, and any new USL or lesion outside the treated area (TA). All results are entered onto the pathology CRF.

All biopsies obtained at the 12 month primary endpoint, and all pathology specimens for recurrent or progressive disease (including biopsies and EMR/ESD/surgical specimens, if applicable) will be independently read by two expert gastrointestinal (GI) pathologists at the lead study site with results entered on a CRF. Any discordance between reviewer results will be resolved with a non-blinded consensus review between the pathologists.

For histopathological interpretation for specimens obtained at baseline or follow-up sessions, as described above, each specimen from each slide will be read out as follows according to the worst cell type observed:

1. Squamous epithelium without intra-epithelial neoplasia
2. Glandular (gastric or intestinal metaplasia) +/- normal squamous epithelium
3. Squamous epithelium with low-grade intra-epithelial neoplasia
4. Squamous epithelium with moderate-grade intra-epithelial neoplasia
5. Squamous epithelium with high-grade intra-epithelial neoplasia
6. Invasive squamous cell carcinoma (depth and grade determined if possible, given limitations of biopsy method versus EMR or ESD)

In a biopsy fragment where multiple grades of intraepithelial neoplasia co-exist, the highest grade will represent the diagnosis for that biopsy fragment. The final subject diagnosis is represented by the worst

histological grade of any fragment for that biopsy session. The study site data will be recorded on a case report form that will include all individual biopsy diagnoses, all lesion diagnoses, and the final subject diagnosis for the individual endoscopy session.

9.2. Subject Screening

If a possibly eligible patient is detected during a regular care endoscopy, a member of the research team will enter those subjects into the provided **screening log**. If the endoscopy fulfills all BQE requirements listed below, this endoscopy is mentioned as the BQE. Additional tests like EUS or CT will be performed if clinically indicated. More detailed eligibility criteria will be assessed by reviewing medical records and subject history.

Baseline Qualifying Endoscopy (BQE)

It is permissible for a site to have performed the baseline qualifying endoscopy prior to a particular subject's enrollment as standard of care, provided the time interval was less than 3 months and at least 1 week prior to primary RFA and all steps as outlined below were completed. Otherwise, the baseline qualifying endoscopy will be performed prospectively.

1. Start WLE to document landmarks and to check all selection criteria that can be assessed endoscopically (e.g. appearance of the lesion, strictures, presence of varices, eosinophilic esophagitis, reflux esophagitis, etc.)
2. Upper endoscopy using Lugol's solution ~1.25% is performed to identify all diseased squamous epithelium of the esophageal body. The only allowable lesions are type 0-IIb.
3. Confirmation of at least one flat (type 0-IIb) USL with a minimum diameter greater than or equal to 3 cm in at least one dimension and greater than 1/4 of esophageal circumference (including a USL mosaic where the entire lesion is at least 3 cm in one dimension). At least one biopsy from at least one such a 'qualifying USL' must demonstrate MGIN or HGIN, and no biopsy can demonstrate ESCC.
4. Confirm that no abnormalities under WLE or Lugol's chromoendoscopy are suspicious for ESCC anywhere in the esophagus (e.g. any non-flat [Paris type 0-I, 0-IIa, 0-IIc, 0-III] abnormalities; 'pink sign' USL, defined as a color change after Lugol's staining: initially whitish yellow and pink 2-3 minutes later). No lesions suspicious for ESCC may exist in the esophagus.
5. Confirmation that the total linear length of the esophagus containing USLs is 12 cm or less is required. This area (plus one additional centimeter proximal and distal) defines the Treatment Area (TA) that will be treated with RFA at the primary RFA session. Only flat type (type 0-IIb) USLs containing LGIN or less may be present outside the TA.
6. Only one continuous TA is permitted per subject, and may by definition include any number of individual USLs. For example, two 4 cm TAs may not be created to treat two separate areas of USLs.
7. The location of the USLs and targeted TA will be documented by obtaining video recordings and still images (with high-resolution endoscopy (optional) and Lugol's staining) of the entire TA at 1 cm intervals. The insertion depth of the endoscope at the proximal and distal margins will be documented in the CRF. Locations of individual USLs are described in the CRF.
8. Biopsies from the BQE and USLs are obtained using standardized localization technique as described in section 10.4.1 and are processed per instructions in section 10.1.1 :

Medtronic Confidential

- Biopsies are obtained first from the distal portion of the esophagus, working proximally so as to minimize obscuring subsequent biopsy targets with blood from the biopsy sites.
- The maximum number of biopsy specimens per specimen jar is 2
 - Targeted biopsies are obtained from each USL and each USL should have a unique jar(s) for its biopsies.

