5.2. Endpoints

5.2.1. Primary Endpoint

The percentage of subjects with “complete response (CR),” defined as complete eradication of squamous histological abnormalities (MGIN or worse) within the treatment area (TA) at 12 months after the initial treatment session (per protocol analysis). Patients who show ESCC in biopsies or resection samples are defined as failures for this endpoint, even if subsequent biopsies at 12 months indicate CR. The primary study hypothesis is that 80% of treated subjects will have a complete response.

Patients

All 100 patients who are included in the cohort will be assessed for the primary endpoint. The run-in patients will not be included for the primary endpoint analysis.

Biopsies

Only biopsies obtained from the original USL bearing portion of the esophagus (the treatment area) will be used in the analysis for the primary endpoint analysis. MGIN or worse noted in any biopsy from outside this region are not considered failures of ablation for the purposes of the primary endpoints.

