If an indication for additional RFA exists, the investigator will determine whether to provide secondary RFA with the circumferential or focal device, based on the extent of disease:

- If lesions involve more than 3/4 of the circumference, circumferential RFA will be used
- If lesions involve less than 3/4 of the circumference, focal RFA will be used
 - It is presumed that all secondary RFA procedures will be performed with the focal device, and this presumption is reflected in Figure 1.

If focal RFA is selected, it is important to note that the effect of Lugol's may significantly wane during the biopsy procedures therefore it may be necessary to reapply the Lugol's in order to target the remaining USLs. Or simply use the biopsy sites for targeting. Each USL is treated so that the ablation effect overlaps at least 5 mm onto the normal staining esophageal mucosa surrounding the USL. The energy density setting is 12 J/cm² and the power density setting is 40 W/cm². Each USL is ablated 3x without changing the position of the catheter. Upon completing focal RFA of USL(s), biopsies are obtained from the TA avoiding all acute RFA sites. Two biopsy fragments are obtained from every 2 cm of the original USL-bearing esophagus that was not treated at this session (see Figure 1).

Example: TA from 30-40, USL bearing esophagus 31-39. One USL at 3 months from 31-32. Sample USL, then RFA USL. Then obtain 2 biopsy fragments from every 2 cm starting at 33-35, 35-37, and 37-39 cm. The area of the USL is avoided (31-33 cm).

In the unlikely event that circumferential RFA is selected for a follow-up RFA, the entire extent of original TA is treated, using same technique as at the primary RFA session.

If necessary, a maximum of four RFA sessions will be performed in total for each patient in this study. If USLs with MGIN or worse in the TA persist after four sessions, the subject is considered a failure for the primary endpoint. Such patients will undergo escape treatment.

Scenario #3: Lesions Suspicious for ESCC Are Present in the TA

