- Central pathology review of biopsies for all biopsies or resection specimens during FU, with independent reading from two pathologists in case of recurrent or progressive disease.
 - Safety assessment

If clinically indicated, Investigator may always perform extra endoscopies in addition to figure 2.

9.4.3. Escape treatment: Endoscopic (EMR or ESD) or Non-Endoscopic Therapy during Treatment or Follow-up Phase

Several indications for escape treatment exist:

[figure not shown]
- Any non-flat lesion (Paris type 0-I, 0-IIa, 0-IIc, 0-III) during treatment or follow-up phase
- Any abnormality under WLE or Lugol's chromoendoscopy that is suspicious for ESCC (e.g. 'pink sign' USL, defined as a color change after Lugol's staining: initially whitish yellow and pink 2-3 minutes later)
- ESCC in biopsies during treatment or follow-up phase (defined as progression of disease)
- Presence of MGIN or worse in any biopsies from TA at the 12 months endoscopy
- Persistent MGIN or worse during follow-up phase despite a maximum of 4 consecutive 3-monthly RFA sessions
- If clinically indicated per Investigator's discretion

Escape treatment can be performed endoscopically (EMR or ESD), or non-endoscopically (surgery, radiotherapy or chemotherapy) per investigator's discretion under the hospital's standards of care. All patients, regardless of treatment used or failure of the primary endpoint, will be followed to study termination for assessment of secondary endpoints:

- Patients who undergo non-endoscopic therapy will be considered a failure for the primary endpoint, but will be tracked through the 5-year follow-up to assess secondary endpoints.
- For patients who undergo endoscopic treatment, final pathology is required:
 - If the disease stage is eligible for endoscopic escape treatment (i.e.: good to moderate differentiation and negative vertical resection margins and m1/m2/m3/sm1 disease and without lymphovascular infiltration), further treatment and/or follow-up endoscopies after the escape treatment will occur according to

Medtronic Confidential

- the study protocol. The application of RFA after endoscopic resection may be performed after minimally 8 weeks later.

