9.10. Definitions

-CR = complete response

Absence of MGIN or worse in biopsies from TA at a single endoscopy.

- Escape treatment

Escape treatment is indicated for lesions with (i) ESCC in biopsies, (ii) non-flat lesions, or (iii) lesions otherwise suspicious for ESCC (e.g. pink-sign positive lesions). Escape treatment will be performed by investigator's distinction and per hospital's standards of care. Subsequent pathology assessment determines whether patient is defined as progressor and failure for the efficacy endpoint.

- Progressive disease

This term is applicable during the whole study. Progressive disease is defined as ESCC in any biopsy or resection specimen. Progressive disease on biopsy will always be treated with escape treatment.

Patients with progressive disease within the first 12 months are a failure for the primary efficacy endpoint, whereas progression patients in subsequent 4 years of follow-up are a failure for the durability endpoint. Progressive disease can be classified into 2 categories based on pathology:

- Eligible for endoscopic treatment, if all of the following characteristics are met: good to moderate differentiation, negative vertical resection margins, m1/m2/m3/sm1 disease and without lymphovascular infiltration.
- Exceeding the limits for endoscopic treatment, if any of the following characteristics was found: poor differentiation, positive vertical resection margins, sm-2 or sm-3 invasion or lymphovascular invasion.

- Treatment failure

This term is applicable to the first 12 months of study. All patients with residual ESCN at the 12 months endoscopy, and patients who progressed to ESCC before 12 months, will be defined as treatment failures.

- Sustained CR

This term is applicable during follow-up, to all patients that were not defined as treatment failures at 12 months. Sustained CR is defined as sustained eradication of MGIN or worse in biopsies from TA, during all FU endoscopies until 60 months.

- Recurrent disease

This term is applicable during follow-up, to all patients that were not defined as treatment failures at 12 months. Recurrent disease is defined as flat (Paris type 0-IIb) USLs with MGIN or HGIN in biopsies from TA during FU, independent of baseline pathology. Recurrent disease will be treated with RFA initially, or escape treatment if persistent, as described in section 9.4.3

10. Risks and Benefits

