7.9.1. Primary Endpoint

The primary endpoint is the percentage of subjects with "complete response (CR)", defined as complete eradication of squamous histological abnormalities (MGIN or worse) within the treatment area (TA) at 12 months after the initial treatment session (per-protocol analysis). Patients who show ESCC in biopsies or resection samples are defined as failures for this endpoint, even if subsequent biopsies at 12 months indicate CR.

The primary study hypothesis is that 80% of treated subjects will have a complete response.

Patients

All 100 patients that are included in the cohort will be assessed for the primary endpoint. The run-in patients will not be included for the primary endpoint analyses.

Biopsies

Only biopsies obtained from the original USL bearing portion of the esophagus (the treatment area) will be used in the analysis for the primary endpoint at 12 months. At 12 months, MGIN or worse noted in any biopsy from outside this region are not considered failures of ablation for the purposes of the primary endpoint.

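### The primary endpoint has two regions: MGIN or HGIN found only in an unstained lesion in a 1 cm treatment margin is excluded by Protocol 5.2.1 and SAP 7.9.1, but counts under the CR definition and the four-session rule

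*Protocol*

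**What the plan says.** **What is treated.** Protocol 9.2 (baseline endoscopy, item 5) takes the length containing USLs, at most 12 cm, and adds a centimeter at each end: "This area (plus one additional centimeter proximal and distal) defines the Treatment Area (TA"). Step 6 of the primary ablation in 9.4.1 requires the ablation zone to cover the whole of this area.

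**What the endpoint text counts.** Protocol 5.2.1 and SAP 7.9.1 both open with eradication within the TA. Their biopsy paragraphs then narrow it. Protocol: "Only biopsies obtained from the original USL bearing portion of the esophagus (the treatment area) will be used in the analysis", followed by "MGIN or worse noted in any biopsy from outside this region are not considered failures of ablation for the purposes of the primary endpoints". SAP: "At 12 months, MGIN or worse noted in any biopsy from outside this region are not considered failures of ablation". The month-12 text of 9.4.1 also says that USLs found outside the USL-bearing esophagus do not enter the primary analysis.

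**What other rules count.** The four-session rule in 9.4.1: "If USLs with MGIN or worse in the TA persist after four sessions, the subject is considered a failure for the primary endpoint". The CR definition in 9.10: "Absence of MGIN or worse in biopsies from TA at a single endoscopy". Treatment failure in 9.10 includes "All patients with residual ESCN at the 12 months endoscopy", with no region stated. The list of escape indications in 9.4.3 includes "Presence of MGIN or worse in any biopsies from TA at the 12 months endoscopy".

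**What is sampled.** Scenario #1 of 9.4.1 (no USLs present) takes routine biopsies from the USL-bearing length, and its example says the 1 cm safety zones are not biopsied at any session. Scenario #2 requires a biopsy of each residual flat USL in the TA and makes no exception for the margins. The month-12 visit uses whichever scenario applies.

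**The concern.** One name covers two lengths of esophagus that differ by 2 cm. Suppose the only MGIN or HGIN at month 12 is in a USL in one of the ablated margins. Under 5.2.1 and SAP 7.9.1 the subject is a complete responder. Under 9.10 the subject is not in CR, and 9.4.3 sends the subject to escape treatment. If that lesion has persisted through four sessions, 9.4.1 also makes the subject a primary endpoint failure.

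The classification carries forward. Secondary endpoints 1, 6, 7, 8 and 9 all start from subjects with CR at 12 months, so their denominators change with it. Endpoint 11, disease outside the TA, does not pick the case up either: if the endpoint exclusion is applied together with the TA of 9.2, margin disease is counted in neither place.

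The direction is fixed. The exclusion can leave the CR rate unchanged or raise it, never lower it. The study is open and single-arm, so the region should be settled before the results are read.

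**Working it through.** **1. The two regions are different lengths.** With a USL-bearing length of L cm, the TA of 9.2 is L + 2 cm and the margin share is 2/(L + 2).

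- First worked example in 9.4.1: USL-bearing 30-36 cm, TA 29-37 cm. L = 6, share 2/8 = 25%.
- Second worked example: USL-bearing 31-39 cm, TA 30-40 cm. L = 8, share 2/10 = 20%.
- At the 12 cm limit: 2/14 = 14.3%.

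These are shares of length, not of risk. The margins contained no USL at baseline and were fully ablated.

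**2. Rules set side by side for MGIN or HGIN in a margin USL.**

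| Rule | Region | Effect |
|---|---|---|
| 5.2.1 and SAP 7.9.1, opening sentence | TA | counts |
| 5.2.1 and SAP 7.9.1, biopsy paragraph | USL-bearing portion | excluded |
| 9.4.1, month-12 sentence on USLs outside | USL-bearing portion | excluded |
| 9.4.1, four-session rule | TA | failure if persistent |
| 9.10, CR | TA | not CR |
| 9.4.3, escape trigger at month 12 | TA | escape treatment |

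Section 9.4.1 is on both sides. Its month-12 text sends persistent USLs within the TA to Scenario #2 and sets aside USLs outside the USL-bearing esophagus. A persistent margin USL fits both descriptions.

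**3. Who can be affected.** Routine biopsies never sample a margin, so a normally stained margin yields no tissue. ESCC is a failure in 5.2.1 with no region named. What remains is MGIN or HGIN in a margin USL biopsied under Scenario #2, in a subject with no other MGIN or worse in the TA.

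**4. The plan's precision.** Half-width = 1.96 × √(p(1 − p)/100). At p = 0.80 this is 7.8 points and at p = 0.90 it is 5.9 points, which reproduces the 6%-8% in Protocol 13.2 and SAP 6.

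**5. Size.** With k margin-only subjects among 100 analyzed, CR over the whole TA is k points below CR over the USL-bearing portion. The documents do not give k; I assume 0 to 5. Start from 82/100, the month-12 rate that Protocol 6.2 cites for this regimen (itself from 17 patients), with exact (Clopper-Pearson) 95% intervals:

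| k | CR over whole TA | 95% CI |
|---|---|---|
| 0 | 82/100 | 73.1-89.0 |
| 3 | 79/100 | 69.7-86.5 |
| 5 | 77/100 | 67.5-84.8 |

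At k = 0 the two readings agree.

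**The case against.** The strongest reply is that the texts governing what enters the month-12 analysis are consistent: the biopsy paragraphs of 5.2.1 and SAP 7.9.1 and the month-12 exclusion in 9.4.1 all use the USL-bearing portion. On this view 9.10 is a general definition, 9.4.3 is a clinical trigger that need not match an analysis rule, and the SAP contains neither the 9.10 definition nor the four-session rule. Part of this stands. The SAP does state a biopsy rule, so a reader should not infer that the region is wholly open to choice after the data are seen. It does not remove the conflict: the four-session rule is written expressly for the primary endpoint, and the opening endpoint sentence in both documents says TA.

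Second, the safety-zone bar is worded for every session. Read literally, no margin tissue would exist and the two regions would give the same result. But the bar sits in the example for Scenario #1, where no USL is present, and Scenario #2 asks for a biopsy of each residual USL in the TA. The bar narrows the problem to targeted biopsies; it does not close it.

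Third, a margin USL first seen at month 12 is arguably neither persistent nor residual, so the four-session rule and the treatment-failure label may not reach it. That is fair. The CR definition and the escape trigger still do, because they refer to any MGIN or worse in TA biopsies.

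Finally, one could align everything to the USL-bearing portion instead. That would be coherent. It fits less well, because calling findings outside the region not failures of ablation suits untreated mucosa, and the margins were ablated.

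**Conclusion.** The plan is wrong as written on this point: it gives contradictory rules for scoring the same biopsy in the primary endpoint. This is more than missing detail. The scope is narrow, namely subjects whose sole MGIN or HGIN is in a margin USL biopsied under Scenario #2. Each such subject shifts CR by 1 point, assuming 100 subjects are analyzed. The number is unknown and may be zero; 0 to 5 is an assumption.

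Three stronger readings are not supported. Section 9.4.1 as a whole does not count margin disease as failure, because it is split. Cancer in a margin cannot be scored as response, because 5.2.1 makes ESCC a failure without a region limit. The 82 versus 79 example does not show a changed conclusion about the 80% hypothesis: k = 3 is illustrative, the plan reports a rate with a 95% CI and specifies no test against 80%, and both intervals include 80%.

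**What to change.** Before the primary analysis, use one region in Protocol 5.2.1, the month-12 text of 9.4.1, 9.10 and SAP 7.9.1. I would choose the TA of 9.2: the USL-bearing length plus 1 cm at each end. It was ablated, and it is the region of the opening endpoint sentence, the CR definition, the four-session rule and the escape trigger. Do not define it by the tattoo line, which is placed at least 1 cm beyond the outermost USL and may lie further out.

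- In 5.2.1 and SAP 7.9.1, remove the equation of the USL-bearing portion with the TA, and state that MGIN or worse in any biopsy from the TA is a failure.
- In the month-12 text, set aside only USLs outside the TA.
- State that the safety-zone bar covers routine biopsies only, so that a margin USL is biopsied under Scenario #2 and counted.
- Report CR for the USL-bearing portion alone as a sensitivity analysis.
- For subjects already past month 12, classify margin biopsies by their labelled location and list any margin USL that was not biopsied.

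The cost is wording and one table. No visit is added, since Scenario #2 already requires these biopsies and labels them by location. The downside is that CR can only stay the same or fall, and some counted failures may be new disease in mucosa that stained normally at baseline. The sensitivity analysis shows how many subjects change status.
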